2.10 Rationale for the Study

Although ibrutinib has shown significant efficacy in CLL and NHL as a single agent, relapses have occurred via binding site mutations and certain subgroups of each disease continue to lag in PFS. Additionally, this treatment requires continuous treatment and does not produce complete remissions. Thus, efforts to diminish the frequency of ibrutinib relapse and also increase the depth of remission with combination based therapies is a priority moving forward in the field of CLL and NHL. In both CLL and NHL the importance of BTK as a true therapeutic target has been genetically, pharmacologically, and clinically validated. Preclinical and clinical data have shown that CLL and NHL are susceptible to single-agent cytotoxicity by selinexor. Selinexor has been shown to inhibit the BCR pathway in an alternate way than ibrutinib by depleting BTK protein level, which provides rationale to combine these drugs. Indeed, targeting a kinase/protein/pathway in two or more different ways is a classic pharmacologic strategy to prevent emergence of drug resistance. In phase I clinical trials in this population, selinexor has shown tolerability and early signals of clinical efficacy. Ibrutinib which is approved for NHL and CLL has similar promising results. We hypothesize the combination will be active and tolerable in this population and want to proceed with phase I investigation. Ultimately, we anticipate this approach moving to larger randomized phase II trials comparing the combination treatment to monotherapy with ibrutinib.

2.11 Rationale for the Dose/Dosing Schedule

Recent analysis of the existing PK data from Phase 1 trials KCP-330-001 and KCP-330-002 supports the use of fixed rather than BSA-based dosing. The 5th and 95th percentile for BSA values encountered to date in Phase 1 trials KCP-330-001 and KCP-330-002 are 1.5 and 2.3 m², respectively (N=331). PK values (C_{max} and AUC^(0-∞)) for a given flat (fixed) dose of selinexor were similar across this typical BSA range, indicating that exposure is not strongly correlated with BSA.

In Phase I study, the lowest dose that selinexor inhibits XPO1 completely for ~24 hours is 12mg/m² (about 20 mg) on a 10 doses per cycle schedule, however, prolonged inhibition of XPO1 mRNA were observed at doses >23 mg/m², allowing twice weekly dosing. Therefore, 40 mg weekly will be our lowest dose administered, with goals to use twice weekly dosing if

tolerated. The phase I study has reached a dose level of 60mg/m² twice weekly, and our proposed study's top dose level (100 mg twice weekly) is equivalent to this dose. We are starting at this lower dose of selinexor to assure tolerability of the combination.

The starting dose of 420 mg of ibrutinib for CLL patients is based on the standard recommended dosing from the phase II study of patients with relapsed/refractory CLL. In this study, correlative analyses demonstrated a greater than 90% occupancy of the pharmacodynamics BTK probe and similar response rates between the groups that received 420 mg and 840 mg, which provided support for the use of the 420 mg dose in CLL patients⁸.

The starting dose of 560 mg of ibrutinib for NHL patients is based on the standard recommended dosing from the phase I study of patients with relapsed/refractory lymphoid malignancies. In this trial, pharmacodynamic studies indicated that a fixed continuous dose of 560mg daily led to full BTK occupancy in a range of individual body weights and was well tolerated, leading to the selection of this dose for phase II studies¹³.

2.12 Correlative Studies Background

We plan to evaluate the inhibition of the B-cell receptor signaling pathway via assessment of phosphorylation of BTK, PLC γ , AKT, and ERK in patients with relapsed or refractory CLL who receive the combination of selinexor and ibrutinib. In primary CLL cells, ibrutinib has been shown to inhibit these components of the B-cell receptor signaling pathway¹². In CLL patient samples with unmutated IgVH status, XPO1 inhibition with selinexor prevents CpG-induced phosphorylation of ERK and AKT, thereby preventing expression of cMyc and cyclin A2 and downstream proliferation of these CLL cells. Selinexor induced BTK downmodulation in CLL cells. Selinexor abrogated phosphorylation of AKT and ERK in primary CLL cells, possibly through targeted inhibition of AKT or ERK pathways⁴⁰. Evaluation of B-cell receptor pathway inhibition in patients on this trial will provide evidence for potential drug synergy or interactions.

We plan to evaluate the change in localization of tumor suppressor proteins in patients with relapsed or refractory CLL following treatment with selinexor with the aid of confocal microscopy and immunoblot of downstream targets of these proteins (NFkB, Mcl1, Tcl1, BTK, p21, BCLxL, cMyc). As selinexor inhibits the exportation of nuclear tumor suppressor proteins⁴⁰, this correlative study will allow exploratory investigation of potential drug interactions on this clinical trial.

Baseline characteristics of tumor samples, plasma and microenvironment will be assessed at baseline to preliminary examine for features of primary resistance. For patients who respond to therapy and then relapse, we will characterize the features of resistance to ibrutinib and selinexor. As both of these are irreversible inhibitors, we will focus on the primary target (BTK, XPO1) and also down-stream molecules (PLC γ 2). We will also take a more global approach through examination of next generation sequencing methods examining the genome, transcriptome, and epigenetic changes from baseline samples to those obtained at relapse. Expression and biochemical studies of pathways of resistance will also be pursued. For CLL this will be done on blood, bone marrow aspirate, and lymph nodes (when available). For NHL, this

will be examined predominately from nodal material (including archival material if available from previous biopsy) along with blood/marrow if positive for NHL. Buccal swabs or other germ line material (marrow fibroblasts, saliva) will be collected for interpretation of next generation sequencing data differentiation of SNP versus acquired mutations.

We also plan to characterize plasma pharmacokinetics of selinexor and steady-state plasma concentrations of ibrutinib. We will compare selinexor pharmacokinetics (full 24-hour profiles) in the absence and presence of ibrutinib, and we will compare ibrutinib steady state concentrations with historical data to identify any significant differences in pharmacokinetics since there is a small potential for drug-drug interactions via CYP3A4/5. We will also characterize concentration vs. time of selinexor in white blood cells. These cells will be obtained from samples collected at the same time points as the plasma pharmacokinetic samples for selinexor. Given KPT-330 chemically reacts with glutathione and may also be metabolized to form glutathione and glucuronide conjugates, we hypothesize intracellular conjugation will vary among patients, and intracellular selinexor exposures will better correlate with pharmacodynamic measures and clinical response to this agent relative to plasma exposures. In addition to selinexor, we will also measure and pseudo-quantify selinexor hydroxylated and conjugated (glutathione and glucuronide) metabolites. The ratio of intracellular metabolites to parent drug may be expected to be higher at baseline or to increase during the first few weeks of combined therapy for patients less sensitive or resistant to selinexor.

A single whole blood sample or lymph node aspirate and buccal swab will be obtained for DNA extraction. DNA will be extracted and stored for potential analysis later if patients relapse on therapy or if relevant pharmacogenetic questions arise during clinical development of selinexor.

3. PATIENT SELECTION

3.1 Eligibility Criteria

3.1.1 Patients must have:

- A histologically confirmed diagnosis of CLL/SLL/B-cell PLL according to the International Workshop on CLL/SLL/B-cell PLL or variant of these [IWCLL¹⁴ or World Health Organization (WHO) Criteria] and meet criteria for treatment or have need for cytoreduction for stem cell transplantation or alternative cell therapy.

OR

A histologically confirmed diagnosis of mantle cell lymphoma (MCL) or diffuse large B-cell lymphoma (DLBCL) de novo or in the setting of transformation from an indolent lymphoma (including DLBCL not otherwise specified) according to the World Health Organization criteria for diagnosis of NHL.

AND

- Patients must have received at least one prior therapy for CLL or NHL, need additional treatment (or have need for cytoreduction as mentioned above), and meet criteria for relapsed or refractory disease. They may not be a candidate for curative therapy. **Relapsed disease** is defined as a patient who previously achieved a CR or a PR, but after a period of six or more months demonstrates evidence of disease progression. **Refractory disease** is defined as progression within six months of the last anti-leukemic or anti-lymphoma therapy, or any response less than a CR or PR.

EXCEPT

- Patients in Cohort 3 (selinexor added to ibrutinib for patients receiving frontline therapy) must be receiving ibrutinib as their initial therapy for CLL or SLL. These patients must have been receiving ibrutinib for at least 1 year before enrollment

3.1.2 Patients must be ≥ 18 years of age.

3.1.3 Patients must have an Eastern Cooperative Oncology Group (ECOG) performance status of < 2 . (See Appendix A.)

3.1.4 Patients with NHL must have objective, documented evidence of disease prior to study entry.

3.1.5 Patients must have normal organ function defined as:

- Platelet count $\geq 50,000/\text{mm}^3$ in the absence of bone marrow involvement; patients with bone marrow involvement only require a platelet count of $\geq 30,000/\text{mm}^3$
- Absolute neutrophil count $\geq 1000/\text{mm}^3$ in the absence of bone marrow involvement; patients with bone marrow involvement are not required to have a minimum absolute neutrophil count
- Creatinine clearance [as calculated by Cockcroft Gault equation= $(140-\text{age}) * \text{Mass (kg)} * (0.85 \text{ if female}) / (72 * \text{creatinine mg/dL}) \geq 30\text{mL/min}$]
- AST/ALT < 2.5 times upper limit of normal (ULN)
- Total bilirubin $\leq 2.0 \times \text{ULN}$.

- 3.1.6 Female patients capable of reproduction and male patients who have partners capable of reproduction must agree to use an effective contraceptive method during the course of the study and for -1 month following the completion of their last treatment. Acceptable methods of contraception are condoms with contraceptive foam, oral, implantable or injectable contraceptives, contraceptive patch, intrauterine device, diaphragm with spermicidal gel, or a sexual partner who is surgically sterilized or post-menopausal.
- 3.1.7 Female of childbearing potential must have a negative serum β -Hcg pregnancy test result within 3 days of first study dose. Female patients who are surgically sterilized or who are > 45 years old and have not experienced menses for > 2 years may have β -Hcg pregnancy test waived.
- 3.1.8 Patients with a history of hepatitis B (surface antigen or core antibody positive and PCR positive) must take lamivudine or equivalent drug during study therapy and for one year after completion of all therapy. Patients on IVIG who are core antibody positive but PCR negative are not mandated to take prophylaxis.
- 3.1.9 Ability to understand and the willingness to sign a written informed consent document.
- 3.1.10 Patients enrolled into cohort 3 must have high-risk disease with higher risk of relapse on ibrutinib. This includes patients with complex karyotype (3 or more cytogenetic abnormalities) or high/very high risk by CLL-IPI (<https://www.mdcalc.com/international-prognostic-index-chronic-lymphocytic-leukemia-ctl-ipi>)

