- 3.2.9 Patients with secondary malignancy that requires active systemic therapy that will interfere with interpretation of efficacy or toxicity of selinexor. (Note: Patients with basal or squamous skin carcinoma, cervical carcinoma in situ, localized breast cancer requiring hormonal therapy or localized prostate cancer (Gleason score <5 are allowed).
- 3.2.10 Patients with active known central nervous system (CNS) involvement of CLL or lymphoma. (Patients with history of CNS CLL or lymphoma now in remission are eligible for the trial.)
- 3.2.11 Patients who are pregnant or breast feeding. (Pregnant women are excluded from this study because it is unknown if selinexor has teratogenic or abortifacient effects. Because there is an unknown but potential risk for adverse events in nursing infants secondary to treatment of the mother with selinexor, breastfeeding should be discontinued if the mother is treated with selinexor.)
- 3.2.12 Patients must have recovered all toxicities from prior therapy or radiation to grade 1 or less (excluding alopecia).

- 3.2.13 Patients may not have had major surgery within 10 days of enrollment, or minor surgery within 7 days of enrollment. Examples of minor surgery include dental surgery, insertion of a venous access device, skin biopsy, or aspiration of a joint. The decision about whether a surgery is major or minor can be made at the discretion of the treating physician.
- 3.2.14 Patients with uncontrolled intercurrent illness including, but not limited to, ongoing or active infection, symptomatic congestive heart failure, unstable angina pectoris, cardiac arrhythmia, or psychiatric illness/social situations that would limit compliance with study requirements.
- 3.2.15 Patients enrolling in Cohort 3 must not have ongoing Grade 3 or higher toxicity due to ibrutinib at study entry (except hypertension that is medically managed).

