5. TREATMENT

5.1 Overview

The study will enroll patients with CLL and NHL in a dose escalation and subsequent expansion. First, patients with relapsed or refractory disease will be enrolled in a dose finding study that will assign doses for each patient using a modified continuous reassessment method using software developed by Piantadosi (Modified Continual Reassessment Method, version 4.0). Up to 10 patients with CLL and 10 patients with NHL will be treated at the estimated MTD as part of the expansion.

In August 2016 after 2 patients were treated at dose level 2 for 1 cycle, both reported significant fatigue and anorexia. While not technically DLT, these AEs were concerning to the investigators, and after discussion with the DSMC it was decided to return to dose level 1 for continued expansion. This was discussed with Karyopharm, who reported increased tolerability

and efficacy using once weekly dosing strategies in other studies.

Cohort 3, which will initiate after the dose escalation and expansion, will add selinexor administered weekly (days 1, 8, and 15 of each cycle) at 40 mg PO, to patients receiving ibrutinib as frontline therapy for at least 12 months. Selinexor plus ibrutinib will be administered for 14 cycles, with discontinuation of selinexor after 14 cycles. At the end of 14 cycles, patients who achieve a minimal residual disease (MRD) negative response may have both drugs discontinued at the discretion of the treating physician. Patients who are MRD positive at the end of 14 cycles will discontinue selinexor and are recommended to continue ibrutinib.

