13.2 Sample Size/Accrual Rate

For cohort 1 and 2, with groups of 2-3 patients per month enrolled in the dose finding study, it is expected that approximately 9 groups of patients will be treated over 18-30 months. Expansion at the MTD is expected to accrue over 6-12 months. Thus, the total study duration is estimated to be 24-42 months. On average, we expect 32 patients to be enrolled, but the total sample size could be as many as 50 patients and will depend on the dose escalation and composition of CLL and NHL patients treated at the estimated MTD as part of the dose-finding portion of the study.

Cohort 3 will be a pilot study to gain data on the ability of selinexor to deepen responses with ibrutinib. Ten patients who have been treated with ibrutinib as their frontline therapy for CLL/SLL for at least 12 cycles and have obtained PR will be accrued to this cohort, and selinexor will be added to ibrutinib for 14 more cycles. The deepening of response rate is defined as the percentage of patients who convert to a MRD negative complete response (MRD- CR) from PR at the end of 14 cycles of selinexor plus ibrutinib among this cohort. If we observe 3 or more patients out of 10 who achieve the conversion from PR to MRD-CR, we will consider this regimen promising and move it forward for further study. For various true deepening of response rates, the table below shows the probability of observing at least 3 MRD-CRs in 10 patients. For example, if the true deepening response rate is 30%, then the probability of declaring the regimen promising is 61.7% with 10 patients.

True Deepening of Response Rate	Probability of Observing 3 or More MRD-CR in 10 Patients
0.1	0.070
0.2	0.322
0.25	0.474
0.3	0.617
0.35	0.738
0.4	0.833

With an accrual rate of 2 patients per month, we expect accrual to be complete in 5 months.

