13.5 Definition of Secondary Endpoints

13.5.1 Toxicity will be graded by CTCAEv4.0. A copy of the CTCAE version 4.0 can be downloaded from the CTEP web site
http://ctep.cancer.gov/protocolDevelopment/electronic_applications/ctc.htm.

13.5.2 Clinical response and survival will be measured by:

- International Working Group Criteria for NHL patients.
- IWCLL 2008 Guidelines for CLL patients.

Response criteria are detailed in Section 10.

Responders will be defined as those with complete response (CR) or partial response (PR). Overall response rate (ORR) will be calculated as the number of evaluable responders divided by the total number of evaluable patients and will be analyzed by cohort. All patients who receive at least one dose of study medication will be included in the ORR and progression free survival.

Progression Free Survival (PFS): PFS will be calculated from the date of study enrollment to disease progression or death, whichever occurs first. Patients who do not progress or die will be censored at the time of last contact with response assessment by physical exam and laboratory studies.

Overall Survival (OS): OS will be calculated from the date of study enrollment to death. Patients who do not die will be censored at the time of last contact. This will be analyzed in each cohort independently.

13.5.3 Response as related to chronic lymphocytic leukemia (CLL) karyotype and IgVH mutational status. Response criteria are detailed in Section 10.

13.5.4 For Cohort 3, the rate of deepening of response is defined as the percentage of patients who attain a MRD negative complete response (MRD- CR) at the end of 14 cycles of selinexor plus ibrutinib.

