13.8.2 Clinical Response and Survival

The degree of response will be summarized within each disease group and at each dose level. ORR will be presented for those patients treated at the MTD with an exact 95 % confidence interval. Also among patients who are treated at the MTD, PFS and OS will be described using Kaplan-Meier curves for each disease group. In cohort 3, the deepening of response rate will be calculated as percentage of patients who achieve MRD-CR, and will be provided with an exact 95% confidence interval.

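### Cohort 3 eligibility omits the partial response at entry that Section 13.2 assumes, and Sections 13.5.4 and 13.8.2 drop it from the endpoint

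*Combined protocol and SAP*

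**What the plan says.** **Entry.** Section 13.2 describes the ten patients as treated with frontline ibrutinib "for at least 12 cycles and have obtained PR will be accrued to this cohort". The sections that govern enrolment do not say this:

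- Section 3.1.1, Cohort 3 exception: ibrutinib must be the initial therapy, and "These patients must have been receiving ibrutinib for at least 1 year before enrollment".
- Section 3.1.10: "Patients enrolled into cohort 3 must have high-risk disease with higher risk of relapse on ibrutinib".
- Section 3.2.15: "Patients enrolling in Cohort 3 must not have ongoing Grade 3 or higher toxicity due to ibrutinib at study entry", apart from managed hypertension.
- Section 5.1: selinexor is added "to patients receiving ibrutinib as frontline therapy for at least 12 months".

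None of these mentions response on ibrutinib. Section 4 asks for source documents for each inclusion and exclusion criterion. Section 13.3 evaluates for response any eligible patient who has had at least one dose of each drug.

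**Endpoint.** Section 13.2 defines the deepening rate as "the percentage of patients who convert to a MRD negative complete response (MRD- CR) from PR at the end of 14 cycles" and applies the 3-of-10 rule to those conversions. Section 13.5.4 defines it as "the percentage of patients who attain a MRD negative complete response (MRD- CR) at the end of 14 cycles". In Section 13.8.2, "the deepening of response rate will be calculated as percentage of patients who achieve MRD-CR". The last two have no condition on status at entry.

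**The concern.** The endpoint is a change from a stated starting point, but the enforceable criteria do not fix that point. A site that follows Section 3 correctly could enrol a patient in CR, in MRD-CR or in stable disease. Section 13.3 then makes that patient evaluable for response.

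The 3-of-10 rule is Cohort 3's only stated basis for taking the regimen forward, and its table treats all ten patients as able to convert. With ten patients and a cutoff of three, one misplaced patient changes the probabilities materially. The direction depends on which endpoint wording is used. Under 13.5.4 and 13.8.2, an entrant already in MRD-CR who stays there is a success that selinexor did not produce. Under 13.2, that patient takes one of ten places and cannot be a success. A patient entering in stable disease likewise cannot convert from PR. In each case the observed rate no longer measures what objective 1.2.4 asks, namely whether selinexor deepens the response to ibrutinib.

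**Working it through.** **Inputs.** From Section 13.2: n = 10, cutoff 3, true rates p = 0.10 to 0.40. Assumed, because the documents give no figure: k, the number of the ten who enter already in MRD-CR, and q, the corresponding fraction in the population.

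**Step 1. Reproduce the plan's table.** P(promising) = P(Bin(10, p) ≥ 3).

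At p = 0.10: 1 − 0.9^10 − 10(0.1)(0.9^9) − 45(0.1^2)(0.9^8) = 1 − 0.3487 − 0.3874 − 0.1937 = 0.0702.

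| p | Plan | Recomputed |
|---|---|---|
| 0.10 | 0.070 | 0.0702 |
| 0.20 | 0.322 | 0.3222 |
| 0.25 | 0.474 | 0.4744 |
| 0.30 | 0.617 | 0.6172 |
| 0.35 | 0.738 | 0.7384 |
| 0.40 | 0.833 | 0.8327 |

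All six agree. The table is right for ten patients who all start in PR.

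**Step 2. Entrants already in MRD-CR are counted (13.5.4 and 13.8.2 wording).** Assume they remain in MRD-CR through cycle 14. Then P(promising) = P(Bin(10 − k, p) ≥ 3 − k).

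- k = 1, p = 0.10: 1 − 0.9^9 − 9(0.1)(0.9^8) = 1 − 0.3874 − 0.3874 = 0.225.
- k = 2, p = 0.10: 1 − 0.9^8 = 1 − 0.4305 = 0.570.

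**Step 3. They are enrolled but not counted and not replaced (13.2 wording).** Then P(promising) = P(Bin(10 − k, p) ≥ 3). The same formula applies to k entrants in stable disease.

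- k = 1, p = 0.10: 1 − 0.3874 − 0.3874 − 36(0.1^2)(0.9^7) = 1 − 0.3874 − 0.3874 − 0.1722 = 0.053.
- k = 2, p = 0.10: 1 − 0.4305 − 8(0.1)(0.9^7) − 28(0.1^2)(0.9^6) = 1 − 0.4305 − 0.3826 − 0.1488 = 0.038.

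| p | k = 0 | k = 1, counted | k = 2, counted | k = 1, not counted | k = 2, not counted |
|---|---|---|---|---|---|
| 0.10 | 0.070 | 0.225 | 0.570 | 0.053 | 0.038 |
| 0.20 | 0.322 | 0.564 | 0.832 | 0.262 | 0.203 |
| 0.30 | 0.617 | 0.804 | 0.942 | 0.537 | 0.448 |

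**Step 4. The same in terms of a population fraction.** If a fraction q enters in MRD-CR and is counted, the effective rate is q + (1 − q)p. At p = 0.10, q = 0.02, 0.05 and 0.10 give effective rates of 0.118, 0.145 and 0.190. P(promising) is then 0.1045, 0.1670 and 0.2922, against 0.0702 at q = 0.

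**The case against.** The strongest reply is that Section 13.2 settles the matter. It is the only place with a decision rule, it says that patients in PR are accrued, and it counts only conversions from PR. Sections 13.5.4 and 13.8.2 report a rate and carry no go rule. Both use the term deepening of response, which 13.2 has already defined. A reader might infer from Section 3 and 13.5.4 that the plan counts a patient already in MRD-CR as a success. The documents do not support that as a flat statement. It follows only if the looser wording is used for the 3-of-10 decision. Under 13.2 as written, such a patient lowers the chance of a promising result.

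Three further points stand:

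- The size of k is unknown. Section 2.10 says that ibrutinib treatment does not produce complete remissions, which suggests that entry in MRD-CR is uncommon. It does not address entry in stable disease.
- Sites complete an eligibility checklist kept in a separate forms document, which is not available here. It might contain the PR condition.
- A reader might think that a patient who is already MRD-negative at entry is a problem in itself. If that patient is in PR, a move to MRD-CR is a true conversion under 13.2, and Section 5.19 recognises MRD-negative PR as its own category.

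The conflict between sections remains. Section 3 is the text against which eligibility is documented, and 13.5.4 is the formal endpoint definition. Neither matches 13.2.

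**Conclusion.** The inconsistency is real. Section 13.2 requires PR at entry and conversion from PR. Sections 3.1.1, 3.1.10, 3.2.15 and 5.1 do not require PR, and Sections 13.5.4 and 13.8.2 do not require conversion from it. The probability table is arithmetically correct but holds only for ten patients in PR.

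The consequence can go either way. With one or two entrants in MRD-CR, the probability at a true rate of 0.10 moves from 0.070 up to 0.225 or 0.570 if they are counted, or down to 0.053 or 0.038 if they are not. At 0.30, not counting them lowers 0.617 to 0.537 or 0.448. These figures rest on assumed values of k. The documents give no baseline rate, and Section 2.10 suggests that it is low.

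This should be fixed, but it does not threaten the trial's main result. Cohort 3 is a ten-patient pilot for a secondary objective, and the primary endpoint (dose-limiting toxicity) is unaffected.

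**What to change.** 1. Add a Cohort 3 criterion to Section 3: documented PR, not CR, on ibrutinib by Section 11.1.3. PR there is a reduction from values before therapy, which for these patients means before ibrutinib, at least a year earlier. The criterion should therefore call for pre-ibrutinib records together with the CT, marrow and immunophenotyping that the Cohort 3 calendar already schedules before study. The pre-study tests alone cannot establish PR.
2. Do not add a requirement for detectable MRD. PR at entry already excludes MRD-CR, and the extra condition would narrow the population in 13.2 without a basis in the text.
3. Insert the PR starting condition in 13.5.4 and 13.8.2 so that both match 13.2, and add it to the description in 5.1.
4. If a patient not in PR has already enrolled, leave that patient out of both numerator and denominator of the conversion rate and report the case separately. Then either apply the 3-of-10 rule to ten PR patients or restate its probabilities for the number available. With the cutoff kept at three, nine patients give 0.053 and 0.537 at true rates of 0.10 and 0.30, and eight give 0.038 and 0.448.

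With ten PR patients the existing table stands unchanged. The cost is one eligibility line, small edits to the endpoint text, retrieval of historical records and slightly slower accrual. No new visit is needed.
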